8.5.4.5 Pharmacokinetic Endpoints

PK parameters will be calculated, as data permit, following each of the three doses of the first *"ramp-up"* administration visit during Cycle 1 and following the third *"one-shot"* administration visit during Cycle 2.

The following PK variables will be assessed following the 1^{st} and 2^{nd} dose of the first "*ramp-up*" administration visit during Cycle 1: C_{max}, t_{max}, C_{trough}, C_{avg}, AUC_(0-t).

The following PK variables will be assessed following the 3^{rd} dose of the first "*ramp-up*" administration visit during Cycle 1: C_{max}, t_{max}, C_{trough}, C_{avg}, C_{last}, t_{last}, AUC_(0-t), AUC_(0- ∞), %AUC_{ex}, k_e, t_{1/2}, CL, V_{ss}, Vd, AUMC_(0- ∞), MRT. Total AUC following the first "*ramp-up*" administration visit during Cycle 1 will be calculated as the sum of AUC_(0-t) related to each dose.

The following pharmacokinetic variables will be assessed following the 3rd "one-shot" administration visit during Cycle 2: C_{max} , t_{max} , C_{trough} , C_{avg} , C_{last} , t_{last} , $AUC_{(0-t)}$, $AUC_{(0-\infty)}$, %AUC_{ex}, k_e , $t_{1/2}$, CL, V_{ss} , Vd, AUMC_(0-∞), MRT, accumulation ratio (Ro).

8.6 MANAGEMENT AND REPORTING OF ADVERSE EVENTS

8.6.1 Reporting of Serious Adverse Events to the Sponsors

All SAEs, whether or not deemed drug-related or expected, must be reported in the corresponding section of the e-CRF within 24 hours (one calendar day) of awareness. Once the information is saved, a notification e-mail will be automatically generated and sent to the Sponsor's DSM.

SAE Report Forms in paper support will be provided as a backup, to be used only in case of breakdown of the e-CRF System. In such case, the Investigator will be responsible for sending the SAE paper form and inserting the data in e-CRF as soon as the system works again.

Whenever paper SAE report forms are used, they must be submitted by e-mail to the Sponsor's DSM.

The initial SAE entry should include at least the following data:

- A short description of the AE.
- Reason why the AE is categorised as serious (seriousness assessment) according to criteria described in § 8.5.2.7.4.
- Causality assessment (according to the algorithm described in § 8.5.2.7.6).
- Study Code and Patient Identification (patient number) [If paper SAE Report Form is used].

If not already reported, the full description of the event and outcome must follow within 1 working day.

The Sponsor's confirmation of reception of the SAE report must be kept in the patient's records.

Any questions arisen during the processing and medical review of the SAE will be managed by means of electronic queries (i.e. queries in the e-CRF).

Any information provided by the Investigator as a query reply or as a follow-up SAE report will be processed in the same way as the initial SAE report within the required timeframe.

When relevant, the e-CRF pages concerning medical history, concomitant medication and laboratory tests will also be retrieved by the Sponsor's SDSM.

Any further significant information and supporting documentation that may become available (such as copies of laboratory reports, tests, procedures, autopsy evidence of the cause of death, etc.) shall

be provided to the Sponsor's SDSM by email no later than 24 hours after they become known by the Investigator.

8.6.2 Management of Suspected Unexpected Serious Adverse Reactions and other relevant safety issues

For each SAE, assessment of seriousness (according to § 8.5.2.7.4), causality (according to §8.5.2.7.6) will be provided by both, the reporting Investigator and the Sponsor. The assessment of expectedness (according to §8.5.2.7.5) will be done by the Sponsor.

NOTE: The causality assessment given by the Investigator will not be downgraded by the Sponsor. If the Sponsor disagrees with the Investigator's causality assessment, the opinions of both, the Investigator and the Sponsor, will be provided.

SUSARs (Suspected Unexpected Serious Adverse Reaction) are AEs which, cumulatively:

- have a reasonable possibility of causal relationship to the IMP
- are serious
- are unexpected

The Sponsor will ensure that all SUSARs occurred during the study are reported on an expedited basis (7 days or 15 days) to the concerned national CAs and ECs, according to European and/or country-specific legal requirements:

- For fatal and life-threatening SUSARs: the Sponsor should report at least the minimum information, as soon as possible, and in any case no later than 7 days after being made aware of the case. If the initial report is incomplete, the Sponsor is to submit a completed report based on the initial information within an additional 8 days.
- SUSARs which are not fatal and not life-threatening are to be reported within 15 days.
- The clock for expedited initial reporting (day zero) starts as soon as the information containing the minimum reporting criteria has been received by the Sponsor (or the Sponsor's delegate).
- If significant new information on an already reported case is received by the Sponsor, the clock starts again at day zero (i.e. the date of receipt of new information). This information should be reported as a follow-up report within 15 days.

The Sponsor will also inform all investigators. Whenever practicable, the information will be aggregated in a 6 monthly cumulative 'line listing' of SUSARs (with a brief safety assessment report), as required, per country regulations.

Apart from SUSARs, the following safety issues will be subjected to expedited management for the identification of possible necessary actions:

- SAEs associated with the study procedures;
- Potential clinically significant findings emerging from non-clinical studies;

• An anticipated end or suspension for safety reasons of another study with the same study drug.

8.6.3 Management of Non-Serious Adverse Events (NSAES) and/or Laboratory Abnormalities

The Investigator must record all the available information concerning any NSAE (whether or not deemed related to the investigational drug) in the corresponding section of the eCRF: eCRF-AE pages, within 5 calendar days after the first knowledge of the occurrence of the event.

When relevant, e-CRF pages concerning medical history, concomitant medication and laboratory test will also be retrieved by the Sponsor's SDSM.

In addition, during the clinical study, abnormalities in laboratory tests (newly occurring after ICF signature or worsening of previously known abnormalities), which are considered clinically significant by the Investigator (such as values significantly above or under normal range or which require an intervention or diagnostic tests, or which may result in the IMP discontinuation), should be reported as AEs. Furthermore, all abnormalities in laboratory values should be collected and reviewed by Sponsor on a monthly basis.

8.6.4 Annual Safety Reporting

Once a year throughout the clinical trial, the Sponsor will provide the concerned national CAs and ECs with a safety report (Development Safety Update Report, DSUR), taking into account all new safety information received during the reporting period.

8.6.5 Breaking of the Randomisation Code

Not applicable.

8.6.6 Serious and Non-Serious Adverse Event Follow-Up

After the End of Study Visit or 70 days after last study drug administration whichever occurs last, the Investigator is not requested to actively follow-up the patient unless ongoing SAEs or nonserious AEs of special interest (as per CRC/iDSMB indication) are present. *However, if the Investigator becomes aware of any SAE with a suspected causal relationship to the IMP after the end of the study, the Investigator shall, without undue delay, report the SAE to the Sponsor. These SAEs should be also recorded in the e-CRF as far as it is available. If the e-CRF is not available, the paper SAE form will be used as a backup.*

Patients who have discontinued the treatment for any reason will be followed up for at least 10 weeks after the last drug dose, or until recovery from all toxic effects or longer in case of expected delayed toxicity.

8.7 MANAGEMENT OF POSITIVE PREGNANCY TEST

Pregnancy tests will be performed, if applicable, during Screening Period, at Visit 11, at Visit 27, at Visits 35-38 and at the End of Study Visit. In addition, female patients of childbearing potential are required to undergo a monthly pregnancy test until 6 months from the last study drug administration. Pregnant women are excluded from the enrollment onto the study. In case a patient becomes pregnant during the study period, she shall be discontinued from treatment and the pregnancy followed up until the outcome.

The Investigator is expected to record in the provided "Pregnancy Exposure Report Form" any case of pregnancy occurring in a female patient participating in the study, during the treatment and until 6 months from the last study drug administration. The mentioned form will be sent by e-mail to the Sponsor's DSM within 5 calendar days after being made aware of the pregnancy. The "Pregnancy Exposure Report Form" is distributed to the sites to be used for this purpose.

The Investigator is requested to follow up each case of pregnancy exposure until the completion or termination of the pregnancy. If the pregnancy continues to term, the "Pregnancy Exposure Report Form" must be completed with the outcome (health status of the newborn infant) and sent to the Sponsor's SDSM again within 5 days after the outcome is known. If the pregnancy results in an abnormal outcome (miscarriage or new-born with congenital abnormality and/or stillbirth), in addition to completing the "Pregnancy Exposure Report Form", this will be recorded in the e-CRF as a SAE and managed as above described in § 8.6.1.

8.8 INDEPENDENT DATA SAFETY MONITORING BOARD

Starting from protocol version 6.1/6.2, an independent Data Safety Monitoring Board (iDMSB) made by a panel of independent AML experts is introduced. In the Step 1, the iDSMB will be

responsible to review dose escalation data and make dose escalation decisions; moreover, the iDSMB will review and assess the data collected during the Step 2 of the study. Roles and responsibilities of the iDSMB are detailed in a separate DSMB Charter.

> Confidential Menarini Ricerche S.p.A

9. STATISTICAL METHODS AND DETERMINATION OF SAMPLE SIZE

9.1 **DETERMINATION OF SAMPLE SIZE**

Due to the nature of the study, no formal sample size calculation is applicable.

Starting from protocol version 6.1/6.2, up to approximately 6 DLT evaluable patients per dose level will be treated with MEN1112 during the dose escalation phase, while up to approximately 30 patients will be treated in the cohort expansion phase. Considering that the patients no-DLT evaluable during the dose escalation phase will be replaced, and assuming a drop-out rate of 30%, up to approximately 60 patients will be treated with MEN1112. This number might be higher in case additional intermediate dose levels will be investigated.

9.2 ANALYSIS POPULATIONS

The following analysis populations will be considered in the statistical analysis:

- Safety population: all patients receiving study drug.
 - DLT population:

Starting from protocol version 6.1/6.2 and following amendments:

- All patients receiving at least 80% of the scheduled study drug administration during the first treatment cycle and with a safety follow-up of at least 6 days after the last administered dose or having experienced a DLT.
- Efficacy population: all patients completing the first treatment cycle and having a post-cycle peripheral blood lab test and bone marrow aspirate.
- **PP population:** all patients of the efficacy population excluding patients who experience major protocol violation(s).
- **PK population:** all patients receiving the study treatment and with reliable drug assay data relevant for the PK parameter of interest.

9.3 STATISTICAL ANALYSIS

9.3.1 Descriptive statistics

All study variables (with the exception of PK variables) will be presented by cohort, dose and overall, by using the appropriate descriptive statistics according to the variable nature, unless otherwise specified:

- Continuous variables: number of non-missing observations, arithmetic mean, standard deviation (SD), minimum, median, maximum.
- Categorical variables: number of non-missing observations and column percentages (N, %).
- Time to event variables: number of non-missing observations, number and percentage of censored observations, 1st quartile, median and its 95% CI, 3rd quartile, Kaplan-Meier survival curves and event rate every 21 days.

The behaviour over time of study variables will be summarised by cohort and overall as follows:

- Continuous variables: descriptive statistics for each time point and for the absolute/percentage differences to baseline.
- Discrete variables: descriptive statistics for each time point and shift tables to baseline.

The Overall Survival (OS) is calculated as:

- In case of all-cause death:
 - OS = date of death date of first study drug administration + 1.
- In case of censored information not for drop-out:
 - OS = date of end of observation period (i.e. study end / end of survival follow-up) date of first study drug administration + 1.
- In case of censored information for drop-out:
 OS = Last date known alive date of first study drug administration + 1.

9.3.2 Efficacy Analysis

Efficacy analyses will be performed only through descriptive statistics.

9.3.3 Pharmacokinetic Analyses

The PK analysis will be run on the PK population. All PK variables (i.e. serum concentrations and parameters) will be summarized by cohort using the following descriptive statistics:

- Number of non-missing observations (N),
- Arithmetic mean and its 90% CI, SD, coefficient of variation (CV%) and standard error (SE),
- Geometric mean (GM) and its 90% CI and GM CV%,
- Minimum, median, maximum.

The concentration of MEN1112 will be summarized for each scheduled sampling time point (see *Appendix II: Timings of Blood sampling for PK* (see)) using descriptive statistics. Individual serum concentration data versus time will be presented in a data listing and visualized as

individual concentration-time plots. Additional analyses, if deemed appropriate, will be described in the statistical analysis plan.

For descriptive statistics, BLLOQ concentrations at time zero, when the subject has not previously been dosed, will be set to zero. All other BLLOQ values will be substituted by $\frac{1}{2}$ LLOQ value before the calculation of the summary statistics.

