	 shift tables to baseline. Pharmacokinetic Analysis The PK analysis will be run on the PK population. All PK variables (i.e. serum concentrations and parameters) will be summarized by cohort using the following descriptive statistics: Number of non-missing observations (N) Arithmetic mean and its 90% CI, SD, coefficient of variation (CV%) and standard error (SE) Geometric mean (GM) and its 90% CI and GM CV% Minimum, median, maximum The concentration of MEN1112 will be summarized for each scheduled sampling time point using descriptive statistics. Individual serum concentration data versus time will be presented in a data listing and visualized as individual concentration-time plots.

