6.2.4.3 Overview of clinical pharmacokinetics

MEN1112 serum concentrations from Cohort 0.1 mg/kg to Cohort 1.7 mg/kg of ARMY-1 study were measured and an interim PK analysis was performed for 38 subjects after a single IV infusion and for 8 subjects after six consecutive IV infusions. The pharmacokinetics of MEN1112 in human were characterised by a dose-dependent behaviour after both single and repeat dose administration, as shown by a more than proportional increase in AUC_{0-inf} in the dose-range 0.1-2.5 mg/kg. MEN1112 was slowly cleared from the body, with a mean half-life ranging from 10.8 to 41.8 hr and from 12.8 to 146.4 hr after single and repeat dose, respectively. The values obtained for volume of distribution at steady state were similar to total blood volume (i.e. 5 L). Estimates of clearance were also low (0.02 - 0.9 L/hr) and in the range of those reported for other monoclonal antibodies. The magnitude of inter-individual variability in MEN1112 disposition is large in the explored dose-range of 0.1-2.5 mg/kg.

6.3 **RISK BENEFIT ASSESSMENT**

The medical need for AML and MDS is yet highly unmet and new treatments are urgently needed for either disease.

MEN1112 is a defucosylated Monoclonal Antibody with high affinity binding to Bst1/CD157 antigen, which is expressed at high prevalence on both AML and MDS cells.

Due to its ability to deplete AML and MDS blasts, even in the presence of low NK cells percentage, MEN1112 is considered to have the potential to represent a new targeted therapeutic opportunity in both AML and MDS patients. the single agent activity of MEN1112 is under clinical investigation in patients with relapsed or refractory AML in the ARMY-1 trial. In this trial, the MTD of the "*one-shot*" administration schedule has been identified at 1.7 mg/kg following the occurrence of two DLT events in two patients treated at 2.5 mg/kg dose level

. The Sponsor therefore performed an in-depth review of the safety

profile of MEN1112, with a particular focus on the four patients

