14.2 APPENDIX II: TIMINGS OF BLOOD SAMPLING FOR PK & EXPLORATORY TESTS

	STUDY VISIT	NR. Blood sampling for PK & exploratory tests	TIMING
	1, 2		Pre-infusion
		3 each Visit	At the end of infusion
			Pre infusion
		3	At the end of infusion
	5	5	14 h after the end of infusion
	4	1	24 h after the end of last ramp-up
CVCLE 1			44 h after the and of last romp up
CICLEI	5	1	dosing infusion
	6	1	68 h after the end of last ramp-up
	0	1	dosing infusion
	8 9 10	2 each Visit	Pre-infusion
	0, 7, 10		At the end of infusion
	12	2	Pre-infusion
			At the end of infusion
	16	2 2	Pre-infusion
			At the end of infusion
	20		At the end of infusion
		4	Pre-infusion
	24		At the end of infusion
			1 h after the end of infusion
CYCLE 2			6 h after the end of infusion
	25	1	24 h after the end of infusion
	26	1 48 h after the end of infus	
	27	1	72 h after the end of infusion
	28	1	96 h after the end of infusion
	29	1	120 h after the end of infusion
	30	1	144 h after the end of infusion
	31	1	1 week after the end of infusion
	32	1	2 weeks after the end of infusion
End of Treatment	33	1	3 weeks after the end of infusion
	34	1	4 weeks after the end of infusion

NOTE: If any interruption occurs during Cycle 1 and the 3rd infusion of Cycle 2, blood sampling for PK & exploratory tests will also be taken at the time of each infusion interruption and just before each infusion resumption.

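### Section 9.3.3 replaces every post-dose BLLOQ concentration by half the LLOQ with no BLLOQ count and no limit, so the constant drives the geometric mean and 90% CI in heavily BLLOQ rows

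*Combined protocol and SAP*

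**What the plan says.** Section 9.3.3 has two rules for BLLOQ concentrations in descriptive statistics. Before any dose, "BLLOQ concentrations at time zero, when the subject has not previously been dosed, will be set to zero". For the rest, "All other BLLOQ values will be substituted by" half the LLOQ.

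The section then states that "The concentration of MEN1112 will be summarized for each scheduled sampling time point". By cohort, it lists a count of non-missing values, arithmetic mean with 90% CI, SD, CV%, SE, minimum, median and maximum. It also lists the geometric statistics, which the synopsis repeats as "Geometric mean (GM) and its 90% CI and GM CV"%. A substituted value counts as non-missing. No BLLOQ count is listed, and no BLLOQ share is set above which any statistic is withheld. Individual data are also shown: "Individual serum concentration data versus time will be presented in a data listing and visualized as" individual plots.

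PK parameters have their own BLLOQ rule in section 8.5.3: zero before tmax, then omission or truncation, with other values only where there is a pharmacokinetic rationale.

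On how fast concentrations fall, section 6.2.4.3 reports "a mean half-life ranging from 10.8 to 41.8 hr and from 12.8 to 146.4 hr" after single and repeat dosing respectively. The repeat-dose range rests on 8 subjects. Sampling after the Day 36 infusion continues to "4 weeks after the end of infusion" (Appendix II).

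**The concern.** Replacing a few low values by half the LLOQ is harmless. Replacing most of a row is not: the GM then moves towards a number set by the assay, and the spread reflects the share replaced rather than variation between patients. A reader of the table sees an N, a GM and a 90% CI with nothing to show that the row is mainly a constant. A run of such rows looks like a stable residual level measured with good precision.

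Pharmacokinetics after single and repeat doses is a secondary objective, so these tables will be read and possibly reused.

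**Working it through.** The documents give no LLOQ, BLLOQ rate, GM or CI, so there is no figure to reproduce.

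**Inputs.** From the documents: the half-LLOQ rule and 90% level (9.3.3); cohorts of 3 or 6 (8.4.3) and up to about 30 (8.4.4); half-lives and a volume near 5 L (6.2.4.3); sampling times (Appendix II). Assumed: log-normal concentrations with CV 50% or 100% (6.2.4.3 calls variability large without a figure), a 70 kg patient, an LLOQ of 0.01 to 1 µg/mL, and single-exponential decline.

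**Step 1: what the rule returns.** With y = ln(concentration), GM = exp(ȳ) and CI = exp(ȳ ± t(0.95, n−1) × SD/√n). In units of the LLOQ:

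- All BLLOQ, any n: SD = 0, so GM 0.5, CI 0.5 to 0.5, CV 0%.
- n = 3, two BLLOQ and one value of 5: ȳ = (2 ln 0.5 + ln 5)/3 = 0.074, SD 1.329, t 2.920. GM 1.08, CI 0.11 to 10.1.
- n = 6, five BLLOQ and one value of 5: GM 0.73, CI 0.34 to 1.59.
- n = 30, 29 BLLOQ and one value of 5: GM 0.54, CI 0.47 to 0.62.

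Zero width therefore needs every value to be BLLOQ. If each value is BLLOQ with probability p, that chance is pⁿ:

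| p | n = 3 | n = 6 | n = 30 |
|---|---|---|---|
| 60% | 22% | 5% | 0% |
| 80% | 51% | 26% | 0.1% |
| 95% | 86% | 74% | 21% |

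**Step 2: coverage of the true GM.** Log-SD σ = √ln(1 + CV²), which is 0.47 for CV 50% and 0.83 for CV 100%. The true GM in LLOQ units is exp(−σ z_p), where z_p is the normal quantile of the BLLOQ share p. In 40,000 simulated cohorts per cell, values below 1 were set to 0.5 and the CI above was computed; a zero-width CI counts as a miss. Coverage of the nominal 90% CI:

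| Share BLLOQ | CV 100%: n = 3 / 6 / 30 | CV 50%: n = 3 / 6 / 30 |
|---|---|---|
| 20% | 91 / 90 / 89% | 92 / 90 / 82% |
| 50% | 83 / 88 / 89% | 83 / 84 / 57% |
| 60% | 74 / 87 / 90% | 74 / 81 / 51% |
| 80% | 48 / 65 / 5% | 48 / 74 / 57% |
| 95% | 5 / 0 / 0% | 14 / 24 / 0% |

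At CV 100% and n = 6, the median reported GM is 1.01 times the truth at 60% BLLOQ, 1.23 times at 80% and 1.97 times at 95% (0.50 against a true 0.254).

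**Step 3: can such rows occur?** The fraction of the end-of-infusion level left after t hours is 2^(−t/half-life):

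| Half-life | 96 h | 168 h | 336 h | 672 h |
|---|---|---|---|---|
| 12.8 h | 0.55% | 0.011% | about 10⁻⁸ | about 10⁻¹⁶ |
| 146.4 h | 63% | 45% | 20% | 4.2% |

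A dose of 1.7 mg/kg in 70 kg and 5 L gives 1.7 × 70/5 = 23.8 µg/mL. Time to reach the LLOQ is half-life × log₂(23.8/LLOQ). For an LLOQ of 1 down to 0.01 µg/mL this is 59 to 144 h at 12.8 h, and 669 to 1642 h at 146.4 h. At the short end, every sample from 1 week (168 h) onward is BLLOQ. At the long end, at most the 4-week sample (672 h) is.

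**The case against.** A reader might infer that intervals collapse wherever most values are BLLOQ. Step 1 shows otherwise: one quantifiable value in a cohort of 3 makes the interval very wide. At CV 100% and 50 to 60% BLLOQ, the rule is close to nominal for n = 6 and 30 (87 to 90%). That part of the objection stands and limits the point to rows with a large majority BLLOQ, with earlier trouble for n = 3 or CV near 50%.

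It also stands that frequency is unknown. The LLOQ is not in the documents, the 12.8 h half-life is not tied to a dose level, and the half-lives come from one-shot dosing. Calling the problem frequent would go beyond the evidence.

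The plan has partial safeguards: minimum, median, maximum, listings and individual plots. An all-BLLOQ row would show three equal values. But those order statistics are computed after substitution, so half the LLOQ appears as if measured, and a listing does not correct the CI printed in the table. Section 9.5 defers detail to a later SAP, which could repair this. As it stands, the protocol prescribes the substitution and the statistics without a limit.

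**Conclusion.** The concern holds in a limited form. Followed as written, section 9.3.3 produces GMs and 90% CIs driven by the constant once about 80% or more of a row is BLLOQ, and a zero-width CI when all of it is. The coverage figures rest on log-normal data with CV 50 to 100%. Whether such rows occur depends on an undisclosed LLOQ and on where half-lives fall between 12.8 and 146.4 h.

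Two wider inferences are not supported. One is that accumulation, AUC or half-life would be distorted: these follow the separate rule in section 8.5.3, and the accumulation ratio Ro is computed from the elimination rate constant. The other is that the MTD would be affected. DLT and MTD use no concentration summary. The iDSMB does review PK data before escalation, but the documents do not say that it uses these tables.

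The effect is confined to descriptive concentration summaries, but the correction is cheap enough that it should be made.

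**What to change.** In section 9.3.3, and carried into the SAP:

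- Report n and % BLLOQ at every scheduled time point.
- Where the observed BLLOQ share exceeds a pre-stated value, for example one half, give only n, n BLLOQ, median, minimum and maximum, with BLLOQ printed as such. Give no mean, SD, SE, CV, GM or CI.
- Keep half-LLOQ substitution at or below that share.
- Optionally, add a left-censored log-normal estimate where enough values are quantifiable. It has no finite solution when all values are BLLOQ, so it cannot replace the limit.

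The cut-off is a reporting convention and does not guarantee coverage: at n = 30 and CV 50%, coverage is already 82% at 20% BLLOQ and 57% at 50%. The printed BLLOQ share lets readers judge such rows.

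The same edit could state that no GM is given at the undosed time point when values there are set to zero, since the logarithm of zero is undefined.

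The cost is a few sentences, with no change to data collection. The downside is that some late time points will have no mean or CI.
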